#### Changed to:

Efficacy analysis will be carried out on the “All Evaluable Patients” population.

Subgroup analysis will be performed in Cohort A according to prior treatment with platinum, BRCA status (BRCA1 vs. BRCA2), hormonal status (Triple negative vs. HR+), number of advanced chemotherapy lines (~~0-1 vs. 2-3~~, **prior PARPi (Yes vs. No)** and starting dose (7 mg FD vs. 3.5 mg/m^2).

***Subgroup analysis will be performed in Cohorts A+A1 according to prior PARPi (Yes vs. No).***

The tables included in each subgroup analysis are the following:

[...]

- Prior PARPi (**Cohort A**): f
- **Prior PARPi (Cohorts A+A1): g**

### **Listing 11.3.2.5 Characteristics of patients with clinical benefit\***

#### **Original listing:**

Patient	PS / Age	Histology Type	Histology Grade	Hormonal Status (ER +/-; PR +/-; HER2 +/-)	No. of prior lines	No. of advanced prior lines	Prior last therapy		
							Agents	Best response	PFS (months)

Patient	Cycles received	Best response	PFS (months)	OS (months)	DR (months)

#### **Changed to:**

Patient	PS / Age	BRCA status	Histology Type	Histology Grade	Hormonal Status (ER +/-; PR +/-; HER2 +/-)	Sites	No. of prior lines	No. of advanced CT prior lines	Prior Platinum (Y/N)	Best response Prior platinum	Prior last therapy		
											Agents	Best response	PFS (months)

Patient	Initial dose	Cycles received	Best response	PFS (months)	OS (months)	DR (months)

### **Section 11.3.2 Secondary analyses**

#### **Added:**

Figure 11.3.2.8 “Swimmer plot” PFS in Cohort A

[figure not shown]

Figure 11.3.2.9 “Swimmer plot” PFS in Cohort A1

[figure not shown]
[figure not shown]

Figure 11.3.2.10 “Swimmer plot” PFS in Cohort B

### Section 11.3.3 Exploratory Multivariate Analysis

## Section title has been modified.

## Original title:

### 11.3.3 Exploratory Multivariate Analysis

Changed to:

### 11.3.3 Exploratory *Univariate and Multivariate Analyses*

## Original section:

Table 11.3.3.1 Multivariate analysis of response rate

(See list of covariates in section 6.2.2).

Table 11.3.3.2 Multivariate analysis of PFS

(See list of covariates in section 6.2.2).

Table 11.3.3.3 Multivariate analysis of OS

(See list of covariates in section 6.2.2).

**Changed to:**

**Table 11.3.3.1 Univariate analysis of response rate**

(See list of covariates in section 6.2.2).

Table 11.3.3.1 11.3.3.2 Multivariate analysis of response rate

(See list of covariates in section 6.2.2. *Only those covariates with a p-value < 0.10 in univariate analysis and with a 90% of valid observations will be included*).

Table 11.3.3.3 Univariate analysis of PFS

*(See list of covariates in section 6.2.2).*

Table 11.3.3.2 11.3.3.4 Multivariate analysis of PFS

Analysis of Maximum Likelihood Estimates

Variable label	Variable values	DF	Parameter estimate	Standard error	Chi-square	Pr > ChiSq	Hazard ratio	95% Hazard ratio confidence limits

(See list of covariates in section 6.2.2. *Only those covariates with a p-value < 0.10 in univariate analysis and with a 90% of valid observations will be included*).

**Table 11.3.3.5 Univariate analysis of OS**

Variable label	Variable values	DF	Parameter estimate	Standard error	Chi-square	Pr > ChiSq	Hazard ratio	95% Hazard ratio confidence limits

(See list of covariates in section 6.2.2).

**Table 11.3.3.3 11.3.3.6 Multivariate analysis of OS**

Analysis of Maximum Likelihood Estimates								
Variable label	Variable values	DF	Parameter estimate	Standard error	Chi-square	Pr > ChiSq	Hazard ratio	95% Hazard ratio confidence limits

(See list of covariates in section 6.2.2. *Only those covariates with a p-value < 0.10 in univariate analysis and with a 90% of valid observations will be included*).

**Table 12.1.2.1.2 Number of patients and cycles with dosing delay, any relationship**

**Original table:**

	N	%
No. of patients treated		
No. of patients with any dose delay		
No. of cycles administered		
No. of cycles susceptible to be delayed*		
No. of cycles with dosing delay**		
No. of patients with		
No cycles delayed		
1 cycle delayed		
2 cycles delayed		
≥ 3 cycles delayed		

**Changed to:**

	N	%
No. of patients treated		
No. of patients susceptible to have any dose delayed		
No. of patients with any dose delayed		
No. of cycles administered		
No. of cycles susceptible to be delayed*		
No. of cycles with dosing delay**		
No. of patients with		
No cycles delayed		
1 cycle delayed		
2 cycles delayed		
≥ 3 cycles delayed		

**Table 12.1.2.1.4 Number of patients and cycles with dosing delay according to the relationship**

**Original table:**

Reasons for delays	N	%
No. of cycles with dosing delays*		
Treatment-related	X	XX.X
Hematological		
Non-hematological		
Both		
Non-treatment-related		

(\*) Denominator= Number of cycles susceptible to have a delay.

**Changed to:**

Reasons for delays	N	%
Cycles	No. of cycles with dosing delays*	
	Treatment-related	X
	Hematological	XX.X
	Non-hematological	
	Both	
	Non-treatment-related	
Patients	No. of patients with dosing delays*	
	Treatment-related	X
	Hematological	XXX
	Non-hematological	
	Both	
	Non-treatment-related	

(\*) Denominator= Number of patient/cycles susceptible to have a delay.

**Table 12.1.3.2 Number of patients and cycles with dose reduction, any relationship**

**Original table:**

	N	%

No. of patients treated	X	XX.X
No. of patients with any dose reduced		
No. of patients with:		
No PM01183 reduction		
1 cycle with PM01183 dose reduced		
2 cycles with PM01183 dose reduced		
No. of cycles administered		
No. of cycles susceptible to have any dose reduced*		
No. of cycles with PM01183 dose reduced **		
No. of cycles with PM01183 dose reduced (Treatment-related)**		

**Changed to:**

	N	%
No. of patients treated	X	XX.X
No. of patients susceptible to have a dose reduced		
No. of patients with any dose reduced		
No. of patients with:		
No PM01183 reduction		
1 cycle with PM01183 dose reduced		
2 cycles with PM01183 dose reduced		
No. of cycles administered		
No. of cycles susceptible to have any dose reduced*		
No. of cycles with PM01183 dose reduced **		
No. of cycles with PM01183 dose reduced (Treatment-related)**		

**Table 12.1.3.3 Number of patients and cycles with dose reduction according to the relationship**

**Original table:**

Reasons for reductions	N	%
No. of cycles with dose reductions*		
Treatment-related	X	XX.X
Hematological		
Non-hematological		
Both		
Non-treatment-related		

(\*) Denominator= Number of cycles susceptible to have a dose reduction.

**Changed to:**

Reasons for reductions	N	%
Cycles		
No. of cycles with dose reductions*		
Treatment-related	X	XX.X
Hematological		
Non-hematological		
Both		
Non-treatment-related		
Patients		
No. of patients with dose reductions*		
Treatment-related	X	XX.X
Hematological		
Non-hematological		
Both		
Non-treatment-related		

(\*) Denominator= Number of patient/cycles susceptible to have a dose reduction.

**Section 12.2.2 Display of Adverse Events**

**Added:**

Table 12.2.2.10 Treatment-related SAEs. Worst grade by patient

SOC	Preferred Term	Grade 1		...	Grade 4		All*	
		N	%		N	%	N	%
Blood and lymphatic system disorders	Anemia NOS							
	...							
	...							
Cardiac disorders	Arrhythmia NOS							
	...							

(\*) Any grade

Table 12.2.2.11 Treatment-related SAEs. Worst grade by cycle

SOC	Preferred Term	Grade 1		...	Grade 4		All*	
		N	%		N	%	N	%
Blood and lymphatic system disorders	Anemia NOS							
	...							
	...							
Cardiac disorders	Arrhythmia NOS							
	...							

\* Any grade

Table 12.2.2.12 SAEs regardless of relationship. Worst grade by patient

SOC	Preferred Term	Grade 1		...	Grade 4		All*	
		N	%		N	%	N	%
Blood and lymphatic system disorders	Anemia NOS							
	...							
	...							
Cardiac disorders	Arrhythmia NOS							
	...							

(\*) Any grade

Table 12.2.2.13 SAEs regardless of relationship. Worst grade by cycle

SOC	Preferred Term	Grade 1		...	Grade 4		All*	
		N	%		N	%	N	%
Blood and lymphatic system disorders	Anemia NOS							
	...							
	...							
Cardiac disorders	Arrhythmia NOS							
	...							

(\*) Any grade

**Listing 12.2.2.6 Treatment-related grade 3-4 AEs. Worst grade per patient**

**Original Listing:**

Patient id.	Cycle	SOC Name	Preferred term	Grade

**Changed to:**

Patient id.	Cycle	SOC Name	Preferred term	Grade

**Listing 12.2.2.8 Adverse Events grade 3-4 regardless of relationship. Worst grade per patient**

**Original Listing:**

Patient id.	Cycle	SOC Name	Preferred term	Grade

**Changed to:**

Patient id.	<del>Cycle</del>	SOC Name	Preferred term	Grade

**Listing 12.3.1.1 SAEs**

**Original Listing:**

Patient id.	Preferred term code	Adverse event reported (verbatim)	Status	Grade	Relationship	Onset date	Resolved date	Action	Serious criteria

**Changed to:**

Patient id.	Preferred term code	Adverse event reported (verbatim)	Status	Grade	Relationship	Onset date	Resolved date	Action	Serious criteria

**Section 12.4.4 Laboratory Values Over Time**

**Tables:**

- 12.4.4.11 Platelet count time course pattern (summary)**
- 12.4.4.12 Platelet count time course pattern (freqs)**
- 12.4.4.13 Neutrophil count time course pattern (summary)**
- 12.4.4.14 Neutrophil count time course pattern (freqs)**
- 12.4.4.15 AST time course pattern (summary)**
- 12.4.4.16 AST time course pattern (freqs)**
- 12.4.4.17 ALT time course pattern (summary)**

**Original table headers:**

	Dose received			Total
	7 mg FD	6 mg FD	5 mg FD	

**Changed to:**

	Dose received			Total
	7 mg FD / 3.5 mg/m 	6 mg FD / 2.6 mg/m 	5 mg FD / 2.0 mg/m 	

**Table added:**

**Table 11.4.4.18 ALT time course pattern (freqs)**

	Dose received						Total	
	7 mg FD / 3.5 mg/m 		6 mg FD / 2.6 mg/m 		5 mg FD / 2.0 mg/m 			
	N	%	N	%	N	%		
Baseline grade 0								
1st cycle								
Onset day grade 3/4								
≤ 7								
8-14								
≥ 15								
...								
2nd cycle, 3rd cycle ....								
Onset day grade 3/4								
≤ 7								
8-14								
≥ 15								
...								
Total								
Onset day grade 3/4								
≤ 7								
8-14								
≥ 15								
...								
Baseline grade 1, 2 ....								
...								
Total								
1st cycle								
Onset day grade 3/4								
≤ 7								
8-14								
≥ 15								
...								
2nd cycle, 3rd cycle ....								
Onset day grade 3/4								
≤ 7								
8-14								
≥ 15								
...								
Total								
Onset day grade 3/4								
≤ 7								
8-14								
≥ 15								
Peak day grade 3/4								
≤ 7								
8-14								
≥ 15								
Recovery day to grade ≤ 2								
≤ 22								
23-28								
≥ 29								
Duration in days to grade 2								
≤ 5								
6-10								
≥ 11								
Recovery day to grade ≤ 1								
≤ 22								

	Dose received						Total	
	7 mg FD / 3.5 mg/m 		6 mg FD / 2.6 mg/m 		5 mg FD/ 2.0 mg/m 			
	N	%	N	%	N	%	N	%
23-28 ≥ 29								
Duration in days to grade 1 ≤ 5 6-10 ≥ 11								

### Listing 12.5.2.3 Troponin I and Troponin T values. Evolution during the study.

#### Original listing:

Patient id.	Cycle	Value	ULN

#### Changed to:

Patient id.	Cycle	Test	Value	ULN

**Table 12.6.1 Concomitant medication during treatment (ATC1, ATC2 and ATC4 levels)**

#### Original table:

Concomitant medication at baseline	N	%
Alimentary tract and metabolism		
Antacids		
Magnesium compounds		
Magnesium adipate		
...		
Blood and blood forming organs		
Antithrombotic agents		
Vitamin K antagonists		
Acenocoumarol		
...		

#### Changed to:

Concomitant medication at baseline	N	%
Alimentary tract and metabolism		
Antacids		
Magnesium compounds		
Magnesium adipate		
...		
Blood and blood forming organs		
Antithrombotic agents		
Vitamin K antagonists		
Acenocoumarol		
...		

**Table 12.6.2 Summary of concomitant medication during treatment**

**Original table:**

	N	%
No. of systems at BL (ATC1 level)		
0		
1		
2		
≥ 3		
Median (range)		
No. of indications at BL (ATC2 level)		
0		
1		
2		
≥ 3		
Median (range)		
No. of agent families at BL (ATC4 level)		
0		
1		
2		
≥ 3		
Median (range)		
No. of agents at BL (PN level)		
0		
1		
2		
≥ 3		
Median (range)		

**Changed to:**

	N	%
No. of systems <del>at BL</del> (ATC1 level)		
0		
1		
2		
≥ 3		
Median (range)		
No. of indications <del>at BL</del> (ATC2 level)		
0		
1		
2		
≥ 3		
Median (range)		
No. of agent families <del>at BL</del> (ATC4 level)		
0		
1		
2		
≥ 3		
Median (range)		
No. of agents <del>at BL</del> (PN level)		
0		
1		
2		
≥ 3		
Median (range)		

**Table 12.6.5 Transfusions and G-CSF by dose**

**Table added:**

**Table 12.6.5 Transfusions and G-CSF by dose**

	7 mg FD		3.5 mg/m^2		Total	
	N	%	N	%	N	%
Transfusions						
RBC						
Platelets						
G-CSF						

Rest of tables in this section has been renumbered.

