### 12.1 Extent of Exposure

Subgroup analysis will be performed according to starting dose (7 mg FD vs. 3.5 mg/m^2). The tables will be annotated by adding a letter as suffix.

The tables included in the subgroup analysis are the following:

Table 12.1.1.1 Number of cycles administered and dose intensity

Table 12.1.2.1.3 Number of patients and cycles with dosing delay according to relationship

Table 12.1.3.3 Number of patient and cycles with dose reduction according to relationship

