### **12.2 Adverse Events**

#### **12.2.1 Adverse Events**

As far as all the toxicities are concerned, the NCI-CTC grade will be used wherever an NCI-CTC grading exists. Otherwise, the severity will be noted. As a convention, the term «Grade» will always be used. Toxicities will be described according to the worst NCI-CTC grade or, for toxicities which do not form the subject of NCI-CTC classification, according to the worst severity.

Adverse events will be described in this section; treatment-related events (stated as related to the study drug or of unknown relationship) will be tabulated.

Type of toxicity and worst grade or severity by cycle and by patient will be summarized according to the Preferred Term coded with MedDRA. Tables will be organized per category of events using System Organ Class of MedDRA.

Subgroup analysis will be performed according to starting dose (7 mg FD vs. 3.5 mg/m^2) and Cohort.

The groups will include:

- Patient treated at 7 mg FD Cohort B
- Patient treated at 7 mg FD Cohort A
- Patient treated at 7 mg FD any Cohort
- Patient treated at 3.5 mg/m^2 Cohort A
- Patient treated at 3.5 mg/m^2 Cohort A1
- Patient treated at 3.5 mg/m^2 any Cohort

The tables will be annotated by adding a letter as suffix.

The tables included in the subgroup analysis are the following:

Table 12.2.2.2 Treatment related AEs. Worst grade by patient

Table 12.2.2.3 Treatment related AEs. Worst grade by cycle

Table 12.2.2.4 Adverse events regardless of relationship. Worst grade by patient

Table 12.2.2.5 Adverse events regardless of relationship. Worst grade by cycle

If clinically relevant the outputs could be split by initial dose or any other characteristic.

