## Section 12.1 Extent of Exposure

Added text:

*Subgroup analysis will be performed according to starting dose (7 mg FD vs. 3.5 mg/m^2). The tables will be annotated by adding a letter as suffix.*

*The tables included in the subgroup analysis are the following:*

*Table 12.1.1.1 Number of cycles administered and dose intensity*

*Table 12.1.2.1.3 Number of patients and cycles with dosing delay according to relationship*

*Table 12.1.3.3 Number of patient and cycles with dose reduction according to relationship*

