## Section 12.2.1 Adverse Events

Added text:

*Subgroup analysis will be performed according to starting dose (7 mg FD vs. 3.5 mg/m^2) and Cohort.*

*The groups will include:*

- *Patient treated at 7 mg FD Cohort B*
- *Patient treated at 7 mg FD Cohort A*
- *Patient treated at 7 mg FD any Cohort*
- *Patient treated at 3.5 mg/m^2 Cohort A*
- *Patient treated at 3.5 mg/m^2 Cohort A1*
- *Patient treated at 3.5 mg/m^2 any Cohort*

*The tables will be annotated by adding a letter as suffix.*

*The tables included in the subgroup analysis are the following:*

*Table 12.2.2.2 Treatment related AEs. Worst grade by patient*

*Table 12.2.2.3 Treatment related AEs. Worst grade by cycle*

*Table 12.2.2.4 Adverse events regardless of relationship. Worst grade by patient*

*Table 12.2.2.5 Adverse events regardless of relationship. Worst grade by cycle*

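### Four SAP exposure and supportive-care tables are split by starting dose alone, so their dose columns mix dose with cohort; the dose-by-cohort groups already used for adverse events would separate the two

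*SAP*

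**What the plan says.** SAP 12.1 asks for a starting-dose breakdown of three outputs: "Table 12.1.1.1 Number of cycles administered and dose intensity", "Table 12.1.2.1.3 Number of patients and cycles with dosing delay according to relationship" and "Table 12.1.3.3 Number of patient and cycles with dose reduction according to relationship". Cohort is not mentioned. In SAP 12.6, "Table 12.6.5 Transfusions and G-CSF by dose" shows 7 mg FD, 3.5 mg/m2 and a total, again without cohort.

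SAP 12.2.1 treats adverse events differently: "Subgroup analysis will be performed according to starting dose (7 mg FD vs. 3.5 mg/m 2 ) and Cohort". It lists six groups. At 7 mg FD they begin with "Patient treated at 7 mg FD Cohort B" and "Patient treated at 7 mg FD Cohort A", followed by any cohort. At 3.5 mg/m2 they are Cohort A, Cohort A1 and any cohort. SAP 12.4 repeats the list for laboratory data.

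Other starting-dose comparisons are confined to Cohort A: the efficacy subgroup (SAP 8.9 and 11.3) and the baseline comparison (Table 11.1.12.5).

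Starting dose was set by the protocol version in force at inclusion (Protocol 5.2.1). Nothing was randomised (Protocol 6.5 and 8.2.1).

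**The concern.** Delays, dose reductions, G-CSF and transfusion requirements are safety items that Protocol 7.2 says will be monitored. A reader who sees them side by side for the two starting doses will tend to read the difference as an effect of dose.

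The cohorts in the two columns are not the same, and there are reasons why they might differ at equal dose:

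- Every A1 patient has had a PARP inhibitor. Cohort B excludes patients with a known deleterious BRCA1/2 mutation.
- The design expects different activity in A (null 20%, alternative 40%) and B (null 10%, alternative 25%). Treatment generally runs to progression, so the number of cycles, and with it the opportunity for a delay, reduction, transfusion or G-CSF, may differ by cohort.

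A difference between cohorts could then appear as a dose effect or hide one. At stake is how the descriptive tolerability tables are interpreted.

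**Working it through.** **Step 1. Compare the splits in the current SAP text.**

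| Output | SAP place | Split specified |
|---|---|---|
| Cycles and dose intensity, Table 12.1.1.1 | 12.1 | starting dose |
| Delays, Table 12.1.2.1.3 | 12.1 | starting dose |
| Reductions, Table 12.1.3.3 | 12.1 | starting dose |
| Transfusions and G-CSF, Table 12.6.5 | 12.6 | starting dose |
| Adverse events | 12.2.1 | starting dose by cohort |
| Laboratory abnormalities | 12.4 | starting dose by cohort |

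**Step 2. Infer what the unsplit columns contain.** In the lists of 12.2.1 and 12.4, B appears only at 7 mg FD and A1 only at 3.5 mg/m2. The 7 mg FD column is therefore A+B and the 3.5 mg/m2 column A+A1. This is an inference from the lists; neither document states it outright.

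**Step 3. Illustrate how far case mix alone could move the columns.** The plan gives no figure to reproduce. The cohort-by-dose counts and the G-CSF rates are not in the documents, so they are assumed.

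Inputs:
- Cohort A 53 and A1 20 (Protocol 8.2 targets).
- Cohort B 30 (stopped at its interim), 37 (from the expected total: 110 − 53 − 20) or 64 (target).
- Assumed: 15, 25, 35 or 45 of the 53 Cohort A patients started at 7 mg FD (a7).

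Shares:
- B in the 7 mg FD column: sB = nB / (nB + a7). Lowest 30/75 = 40%; highest 64/79 = 81%.
- A1 in the 3.5 mg/m2 column: sA1 = 20 / (20 + 53 − a7). Lowest 20/58 = 34%; highest 20/28 = 71%.

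With no dose effect in any cohort, and event rates pA, pB and pA1, the expected column difference (3.5 mg/m2 minus 7 mg FD) is

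sA1 × (pA1 − pA) − sB × (pB − pA).

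One case in full, with nB = 37, a7 = 25 and rates of 30% in A, 20% in B and 40% in A1:
- 7 mg FD: (25 × 0.30 + 37 × 0.20) / 62 = 14.9/62 = 24.0%.
- 3.5 mg/m2: (28 × 0.30 + 20 × 0.40) / 48 = 16.4/48 = 34.2%.
- Difference +10.1 points (from unrounded values), with a true dose effect of zero.

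Over all the assumed splits:

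| Assumed rates A / B / A1 | Difference with no dose effect (points) |
|---|---|
| 30 / 30 / 30% | 0 |
| 30 / 30 / 40% | +3.4 to +7.1 |
| 30 / 20 / 40% | +9.6 to +13.0 |
| 30 / 40 / 20% | −9.6 to −13.0 |
| 30 / 40 / 40% | −4.7 to +3.1 |

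**Step 4. Masking.** Take Cohort A split 27/26, B = 30, and need at equal dose of 30% in A and B and 50% in A1. Suppose a true 10-point fall at 3.5 mg/m2 in every cohort. The 7 mg FD column shows (27 × 0.30 + 30 × 0.30)/57 = 30.0%, and the 3.5 mg/m2 column (26 × 0.20 + 20 × 0.40)/46 = 28.7%. A 10-point fall appears as 1.3 points.

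**Step 5. With the split.** In the no-effect scenarios the Cohort A contrast has expected difference zero by construction. That removes the cohort component only.

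**The case against.** The strongest case is that little depends on these tables. They show counts, percentages, medians and ranges, with no test or decision rule. SAP 8.9 describes the starting-dose safety subgroup in terms of laboratory abnormalities and adverse events, and both already carry the six groups. Neutropenia, anaemia and thrombocytopenia, which lie behind much G-CSF and transfusion use, can therefore be compared within Cohort A. This stands, and it is why the point is minor.

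Second, the split is not forbidden. Appendix I shows outputs by cohort, in total, or both; SAP 12.2.1 leaves room for further splits; and patient-level listings of delays, reductions, transfusions and G-CSF would let the Cohort A result be recovered. This is correct, but none of it specifies dose within cohort for these four tables.

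Third, cycle-level delay and reduction percentages use cycles at risk as denominator, and dose intensity is per week, which partly allows for time on treatment. That also stands. Patient-level counts and Table 12.6.5 remain exposed.

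Fourth, prior PARP inhibitor use is not confined to A1, because SAP 8.9 plans that subgroup inside Cohort A too. This weakens the contrast between A and A1 but does not make the columns alike.

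A reader might go further and infer that these tables are the main evidence on whether the later regimen is better tolerated, or that the dose comparison is biased by about 10 points. The documents support neither: they assign the tables no such role, and the event rates are invented for illustration.

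**Conclusion.** The inconsistency is real and the point holds at low severity. As specified, the dose columns of Tables 12.1.1.1, 12.1.2.1.3, 12.1.3.3 and 12.6.5 mix starting dose with cohort, while the adverse event and laboratory tables separate them.

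The size and direction of any distortion are unknown. The 0 to 13 point range, in either direction, rests on assumed rates, an assumed Cohort A dose split and evaluable-patient targets; the tables themselves use all treated patients. It shows what is possible, not what to expect. The A+B against A+A1 make-up is inferred from the group lists. The primary endpoint, its error rates and the stopping rules are not affected.

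It would also be wrong to infer that the Cohort A contrast is a clean dose comparison. Starting dose followed protocol version, so dose remains tied to calendar time even inside Cohort A, and to anything else that changed with it.

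**What to change.** In SAP 12.1 and at Table 12.6.5, state that Tables 12.1.1.1, 12.1.2.1.3, 12.1.3.3 and 12.6.5 will be produced for the same six dose-by-cohort groups as in 12.2.1 and 12.4.

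Add one sentence: any reading of 7 mg FD against 3.5 mg/m2 in these tables is made within Cohort A; the any-cohort columns are descriptive only; and the Cohort A comparison is non-randomised and confounded with calendar time.

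The cost is about two lines of SAP text and reuse of existing table code, with no new data. The Cohort A contrast rests on fewer patients and is less precise than the pooled columns.
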